2. SCHEDULE OF ACTIVITIES (SOA)

Table 1 Double-blind Treatment Phase Procedures: Year 1, Arms A and B

Double-Blind Treatment Phase Procedures	Screening (35 to							- Arms A		. ,				Unsched- uled Visit	Early Withdrawal	Follow- up visit
(D=Day, W=Week)	1 day(s) before D1)	D1 (Base- line)	W4	W6	W8	W12	W16	W20, W24	W26	W28, W32, W36	W40	W44, W48	W52	(1)	Visit (b)	(8 weeks post last dose)
Informed consent	Χ															,
Inclusion and exclusion criteria	Χ	X (m)														
Genetics Informed consent	X (r)															
Randomization		Х														
Assessments: Clinic																
Full physical exam including height and weight	Х															
12-lead ECG	Χ															
Demography	Χ															
Medical history (includes substance usage)	Х															
Past and current medical conditions including cardiovascular medical history	Х															
Vital signs	Х															
Symptom-driven physical exam, vital signs		Х	Х	Х	Х	Х	Х	Χ	Х	Х	Х	Х	Х	Х	Х	Х
Weight		Χ							Χ				Χ		Х	
Assessments: Independent Asse	ssor				•											
SLEDAI-2K: Blinded Assessor (t)		Х				Χ			Χ		Χ		Χ	Χ	Χ	
Assessments: Principal Investiga	ator															
SLEDAI-2K: Investigator	Χ	Х	Х		Χ	Χ	Χ	Х	Χ	Х	Χ	Х	Χ	Χ	Χ	
C-SSRS Baseline/Screening	Χ															
C-SSRS Since Last Visit		Х	Х	Χ	Χ	Χ	Χ	Х	Χ	Х	Χ	Х	Χ	Χ	Χ	Х

Double-Blind Treatment Phase Procedures	Screening (35 to							- Arms A		,				Unsched- uled Visit	Early Withdrawal	Follow- up visit
(D=Day, W=Week)	1 day(s) before D1)	D1 (Base- line)	W4	W6	W8	W12	W16	W20, W24	W26	W28, W32, W36	W40	W44, W48	W52	(1)	Visit (b)	(8 weeks post last dose)
Neurological Assessment	Χ	Χ	Χ	Χ	Χ	Х	Χ	Х	Χ	Χ	Χ	Х	Χ	Х	Х	X
SLE Flare Index (n)		Χ	Χ		Χ	Х	Х	Х	Χ	Χ	Х	Х	Х	Х	Х	
SLICC-ACR Damage Index		Χ											Χ		Х	
Physician Global Assessment (PGA)		Х	Х		Х	Х	Х	Х	Х	Х	Х	Х	Х	Х	Х	
Survival Assessment (d)													Χ			
Assessments: Patient Reported 0	Outcomes (Pl	ROs)														
Patient Global Assessment (c)		Χ			Χ	Χ			Χ		Χ		Χ		X	
FACIT-Fatigue (c)		Χ			Χ	Χ			Χ		Χ		Χ		X	
Lupus QoL (c)		Χ			Χ	Χ			Χ		Χ		Χ		Χ	
WPAI: Lupus (c)		Χ			Χ	Χ			Χ		Χ		Χ		X	
Post-treatment interview (o)													Χ		X	
Central Laboratory Tests																
Drug and alcohol screen	Χ															
HIV, Hep B and Hep C screen	Χ															
Pregnancy test (WCBP) (e)	Χ	Х	Χ	Χ	Χ	Х	Χ	Х	Χ	Χ	Χ	Х	Χ	Χ	X	Х
Laboratory assessments (include liver chemistries)	Х	Х	Χ	Х	Х	Χ	Х	Χ	Χ	Χ	Х	Х	Х	Х	Х	Х
Serum immunoglobulin (IgA, IgM, IgG)	Х	Х	Χ	Х	Х	Χ	Х	Χ	Χ	Χ	Х	Х	Х	Х	Х	Х
Urinalysis	Χ	Χ	Χ	Χ	Χ	Х	Х	Х	Χ	Χ	Х	Х	Х	Х	Х	Х
Anti-dsDNA/ANA, Complement C3/C4	Х	Х	Х		Х	Х	Х	Х	Х	Х	Х	Х	Х	Х	Х	Х
Extractable nuclear antigens (ENAs)		Х			Х				Х				Х		Х	
PT/PTT	Χ	Χ			Χ				Χ				Χ	Χ	Χ	

Double-Blind Treatment Phase Procedures	Screening (35 to					atment			,	. ,				Unsched- uled Visit	Early Withdrawal	Follow- up visit
(D=Day, W=Week)	1 day(s) before D1)	D1 (Base- line)	W4	W6	W8	W12	W16	W20, W24	W26	W28, W32, W36	W40	W44, W48	W52	(1)	Visit (b)	(8 weeks post last dose)
Antiphospholipid antibodies (aCL, lupus anticoagulant, ± beta-2-glycoprotein-1)		Х			Х				Х				Х	Х	Х	,
Labs and Biomarkers																
B cells subsets		Χ	Χ				Χ		Χ		Χ		Χ		X	Χ
BLyS Protein		Χ											Χ		Х	
RNA for Interferon Signature		Χ														
Immunogenicity: Belimumab		Χ	X(f)	X(f)	Χ				Χ				Х	Х	X	Х
Immunogenicity: Rituximab		Χ	X(f)	X(f)	Χ				Χ				Х	Х	Х	
Pharmacokinetics: Belimumab			X(f)		Χ				Χ				Χ	X	X	Χ
Pharmacokinetics: Rituximab			X(g)	X(g)	Χ				Χ	X(h)				Х	Х	Х
Genetic sample		Χ														
Further Research																
Blood Leukocyte Analysis (PBMC) (p)		Χ											Х		Х	
B cell receptor (q)		Χ												Х	Х	
B cells subsets (u)		Х	Х										Х		Х	
Study Treatment																
Training on use of Autoinjector	Х	Χ														
Dispense/Train or Collect Electronic Diary		Χ													Х	
Dispense Belimumab for weekly dosing (SC)		X (i)	X (s)		Х	Х	Х	Х		Х	Х	Х				
Rituximab or Rituximab-Placebo (IV)			X (j)	X (j)										X (j)		
Discontinue immunosuppressants			X	U/										U/		
Initiate corticosteroid taper						X (k)										

Double-Blind Treatment Phase Procedures	Screening (35 to				Tre	atment	Period -	- Arms A	and B	(a)				Unsched- uled Visit	Early Withdrawal	Follow- up visit
(D=Day, W=Week)	1 day(s) before D1)	D1 (Base- line)	W4	W6	W8	W12	W16	W20, W24	W26	W28, W32, W36	W40	W44, W48	W52	(1)	Visit (b)	(8 weeks post last dose)
Target for steroid corticosteroid dose to reach prednisone equivalent ≤5 mg/day									X							,
Study Visit Review Procedures																
AE/SAE review		Χ	Χ	Χ	Χ	Χ	Χ	Χ	Χ	Χ	Χ	Χ	Χ	Χ	Χ	Χ
Concomitant medication review (including SLE medications)	Х	Х	Χ	Х	Х	Χ	Χ	Χ	Χ	Χ	Х	Х	Х	Х	Х	Х
Review HCRU and Patient Diary			Х	Χ	Χ	Χ	Χ	Х	Χ	Х	Χ	Х	Χ	Χ	Χ	

- a. Starting at Week 4 and throughout the study period including follow-up, a study visit time window ± 7 days is acceptable. Note: Every effort should be made to schedule the visit in this window, however if the COVID-19 pandemic situation affects the ability to achieve this then, for those COVID-19 specific instances, the visit window can be expanded to ±28 days.
- Early Withdrawal Visit 1-4 weeks after last dose for participants that withdraw from the study.
- c. To be conducted prior to clinical assessments.
- d. Survival assessment at Week 52 for participants who withdraw before Week 52.
- e. Serum pregnancy test at Screening; Urine pregnancy test at all other visits, including pregnancy test 16 weeks after last dose of belimumab. The pregnancy test 16 weeks after the last dose of belimumab may be done at home, with the results reported by telephone call to the clinic. See Section 9 for pregnancy test requirements.
- f. At Week 4 and Week 6 pre-rituximab/ rituximab-placebo dose.
- g. At Week 4 post-rituximab/rituximab-placebo dose and at Week 6 pre- and post- rituximab/rituximab-placebo dose.
- h. At Week 32 only.
- i. The first dose of belimumab will be administered at the clinic and the subject needs to stay for 3 hours post dose for observation.
- j. Premedication administration will be given 30 minutes prior to each Rituximab / rituximab-placebo dose and the subject needs to stay in clinic for 1 hour post dose for observation (i.e., Clinical monitoring including vital signs). If the subject misses the Week 4 dosing visit and dosing will take place during an unscheduled visit, the first dose of rituximab should be scheduled no later than 7 days after Week 4. The second dose of rituximab must be administered at least 2 weeks but not more than 3 weeks after the first rituximab dose.

 NOTE: Contact Medical Monitor if the date of a) first dose is more than 1 week past week 4, and b) if the date of the second dose of rituximab would exceed 3 weeks after the first dose. During unscheduled visits, procedures for Immunogenicity and PK will follow the schedule for Week 4 and Week 6.
- k. It is recommended that the steroid taper be initiated on Week 12 to reach the target prednisone equivalent of ≤5 mg/day at Week 26, but the taper schedule is at the discretion of the investigator.

- Procedures to be performed at Unscheduled Visits are based on reason for Unscheduled Visit, including adverse event or discontinuation of study agent. Please refer to Section 9.4 and to the guidance provided in the Study Reference Manual.
- m. The interim medical history, including SLE medications, should be reviewed prior to randomization to assure that the participant's eligibility has not changed.
- n. Blood samples for a B cell receptor analysis should be obtained in the event of a suspected SLE Flare (refer to footnote q).
- o. To be conducted at US sites only.
- p. To be conducted only at US study sites.
- q. To be conducted only at US study sites. B-cell receptor samples are also collected at US sites when subjects experience a suspected SLE Flare.
- r. Separate Genetics informed consent as needed per country specific requirements. Genetics informed consent and sample can be obtained any time after baseline.
- s. If a subject happens to be scheduled for an infusion (week 4 and/or 6) on the same day of the week as their normally scheduled belimumab injection, whenever possible, the day of the belimumab injection should be altered within the dosing window to separate the day of the injection from the day of the infusion to allow for appropriate safety monitoring of the infusion. If subject has already self-administered the belimumab dose on the day of IV infusion, contact study Medical Monitor for guidance prior to administering the rituximab/rituximab-placebo dose.
- t. Independent assessor will perform symptom-driven physical examination to include, at a minimum, assessments of eyes, mouth, skin, lungs, cardiovascular system, abdomen, and extremities (including joints). Independent assessors must have a source document (paper record in the study file) where the findings in the clinical exam and laboratory analyses supporting the scoring of S2K are described.
- u. To be conducted only at select European sites

Table 2 Double-blind Observational Phase Procedures: Year 2, Arms A and B

		Observ	vational Perio	d – Arms A	and B (a)				
Arms A and B Double-blind Observational Phase Procedures (W=Week)	W60	W64	W72	W80	W88, W96	W104	Unscheduled Visit (e)	Early Withdrawal Visit (f)	Follow-up visit (8 weeks post last dose) (j)
Assessments: Clinic									
Symptom-driven physical exam, vital signs	Х	Χ	Χ	Х	X	Х	Х	Χ	Х
Weight						X		Χ	
Assessments: Independent Assessor									
SLEDAI-2K: Blinded Assessor (m)		Χ		Χ		X	X	Χ	
Assessments: Principal Investigator									
SLEDAI-2K: Investigator	Χ	Χ	Χ	Χ	X	X	X	Χ	
C-SSRS Since Last Visit	Χ	Χ	Χ	Χ	X	X	X	Χ	X
Neurological assessment	Χ	Χ	Χ	Х	X	Х	Х	Х	Х
SLE Flare Index (g)	Х	Χ	Χ	Х	X	Х	X	Χ	
SLICC-ACR Damage Index						Х		Χ	
Physician's Global Assessment (PGA)	Χ	Χ	Χ	Χ	X	X	X	Χ	
Survival assessment (c)						Х			
Assessments: Patient Reported Outcomes (P	ROs)								
Patient Global Assessment (b)		Χ	Χ			X		Χ	
FACIT-Fatigue (b)		Χ	Χ			X		Χ	
Lupus QoL (b)		Χ	Χ			Χ		Χ	
WPAI: Lupus (b)		Χ	Χ			Χ		Χ	
Exit Interview (h)						Х		Х	
Central Laboratory Tests									
Urine pregnancy test (WCBP) (d)	Χ	Χ	Χ	Χ	Χ	X	Χ	Χ	X
Laboratory assessments (include liver chemistries)	Х	Х	Χ	Х	Х	Х	X	Χ	Х
Serum immunoglobulin (IgA, IgM, IgG)	Χ	Х	Χ	Х	Х	Х	Х	Х	Х
Urinalysis	Χ	Х	Χ	Х	Х	Х	Х	Х	Х
Anti-dsDNA/ANA, Complement C3/C4	Χ	Χ	Χ	Х	Х	Х	Х	Х	Х
Extractable nuclear antigens (ENAs)	Χ			Χ		Χ		Χ	
PT/PTT				Χ		Χ	Х	Χ	

		Obser	vational Perio	d – Arms A	and B (a)				
Arms A and B Double-blind Observational Phase Procedures (W=Week)	W60	W64	W72	W80	W88, W96	W104	Unscheduled Visit (e)	Early Withdrawal Visit (f)	Follow-up visit (8 weeks post last dose) (j)
Antiphospholipid antibodies (aCL, lupus anticoagulant, ± beta-2-glycoprotein-1)	Х			Х		Х	Х	Χ	
Labs and Biomarkers									
B cells subsets	Χ			Х		Х		Х	Х
BLyS Protein	Χ	Х	Х	Х	Х	Х		Х	
Immunogenicity: Belimumab				Х		Х	Χ	Χ	Х
Immunogenicity: Rituximab							Х	Χ	
Pharmacokinetics: Belimumab	Χ	Х	Х	Х			Х	Х	Х
Pharmacokinetics: Rituximab							Х	Х	Х
Further Research									
Blood Leukocyte Analysis (PBMC) (k)				Х		Х		Χ	
B cell receptor (I)						Х	Х	Χ	
B cell subsets (n)	Χ			Х		Х	Х	Χ	
Study Treatment									
Collect Electronic Diary						Х		Χ	
Study Visit Review Procedures									
AE/SAE review	Χ	Χ	Х	Х	Χ	Х	Х	Χ	Х
Concomitant medication review (including SLE medications)	Х	Х	Х	Х	Х	Х	Х	Х	Х
Review HCRU and Patient Diary (i)	Χ	Х	Х	Х	Х	Х	Х	Х	

- a. During this study period including follow-up, a study visit time window ± 7 days is acceptable. Note: Every effort should be made to schedule the visit in this window, however if the COVID-19 pandemic situation affects the ability to achieve this then, for those COVID-19 specific instances, the visit window can be expanded to ±28 days.
- b. To be conducted prior to clinical assessments.
- c. Survival assessment at Week 104 for participants who withdraw before Week 104.
- d. The pregnancy tests 12 months after the last dose of rituximab / rituximab-placebo (Week 58) and 16 weeks after the last dose of belimumab (Week 68) may be done at home, with the results reported by telephone call to the clinic. See Section 9 for pregnancy test requirements for participants that withdraw. (Argentina only: In addition to pregnancy testing at the specified clinic visits, a urine pregnancy test is to be performed at home at Week 56, Week 68, Week 76, Week 84, Week 92, and Week 100, with the results reported by telephone call to the clinic.)
- e. Procedures to be performed at Unscheduled Visits are based on reason for Unscheduled Visit, including adverse event or discontinuation of study agent. Please refer to Section

- 9.4 and to the guidance is provided in the Study Reference Manual.
- f. Participants who withdraw from the study are required to complete an Early Withdrawal Visit 1-4 weeks after withdrawal from the study.
- g. Blood samples for a B cell receptor analysis should be obtained in the event of a suspected SLE Flare (refer to footnote I).
- h. To be conducted at US sites only.
- i. Diary review is only necessary if the patient receive Belimumab rescue therapy.
- j. Follow up visit is required only for subjects who receive belimumab rescue therapy at any time between Week 52 and Week 104.
- k. To be conducted only at US study sites.
- I. To be conducted only at US study sites. B-cell receptor samples are also collected when subjects at US sites experience a suspected SLE Flare.
- m. Independent assessor will perform symptom-driven physical examination to include, at a minimum, assessments of eyes, mouth, skin, lungs, cardiovascular system, abdomen, and extremities (including joints). Independent assessors must have a source document (paper record in the study file) where the findings in the clinical exam and laboratory analyses supporting the scoring of S2K are described.
- n. To be conducted at select European centers.

Table 3 Open-Label Treatment Phase Procedures: Year 1, Arm C

Treatment Phase Procedures	Screening					Trea	atment F	Period –	Arm C ((a)						
(D=Day, W=Week)	(35 to 1 day(s) before D1)	D1, (Base- line)	W4	W6	W8	W12	W16	W20, W24	W26	W28, W32, W36	W40	W44, W48	W52	Unsched- uled Visit (h)	Early Withdrawal Visit (b)	Follow-up Visit (8 weeks post last dose)
Informed consent	Х															
Inclusion and exclusion criteria	X	X (i)														
Genetics Informed consent	X (m)															
Randomization		Χ														
Assessments: Clinic																
Full physical exam including height and weight	Х															
12-lead ECG	Х															
Demography	Х															
Medical history (includes substance usage)	Х															
Past and current medical conditions including cardiovascular medical history	х															
Vital signs	Χ															
Symptom-driven physical exam, vital signs		Х	Х	Х	Х	Х	Х	Χ	Х	Χ	Х	Х	Х	Х	Х	Х
Weight		Х							Χ				Х		Х	
Assessments: Independent As	sessor															
SLEDAI-2K: Blinded Assessor (n)		Х				Х			Х		Х		Х	Х	Х	
Assessments: Principal Invest	igator															
SLEDAI-2K: Investigator	Х	Χ	Χ		Χ	Χ	Χ	Х	Χ	Χ	Х	Χ	Х	Χ	Х	
C-SSRS Baseline/Screening	Х															
C-SSRS Since Last Visit		Χ	Χ	Χ	Χ	Χ	Χ	Х	Χ	Х	Х	Х	Х	Χ	Х	Χ
Neurological Assessment	Х	Х	Χ	Χ	Χ	Χ	Χ	Χ	Χ	Х	Х	Χ	Χ	Χ	Χ	Χ
SLE Flare Index (j)		Χ	Χ		Χ	Χ	Χ	Χ	Χ	Χ	Χ	Χ	Χ	Х	Х	

Treatment Phase Procedures	Screening					Trea	atment F	Period –	Arm C ((a)						
(D=Day, W=Week)	(35 to 1 day(s) before D1)	D1, (Base- line)	W4	W6	W8	W12	W16	W20, W24	W26	W28, W32, W36	W40	W44, W48	W52	Unsched- uled Visit (h)	Early Withdrawal Visit (b)	Follow-up Visit (8 weeks post last dose)
SLICC-ACR Damage Index		Χ											Χ		X	
Physician Global Assessment (PGA)		Х	Х		Х	Χ	Χ	Χ	Χ	Х	Χ	Х	Χ	Х	Х	
Survival Assessment (d)													Χ			
Assessments: Patient Reporte	d Outcomes (PROs)														
Patient Global Assessment (c)		X			Χ	Χ			Х		Х		Х		Х	
FACIT-Fatigue (c)		Х			Χ	Χ			Х		Х		Х		Х	
Lupus QoL (c)		Х			Χ	Χ			Χ		Χ		Х		X	
WPAI: Lupus (c)		Х			Χ	Χ			Х		Х		Х		Х	
Treatment Interview (k)													Х		Х	
Central Laboratory Tests																
Drug and alcohol screen	Χ															
HIV, Hep B and Hep C screen	X															
Pregnancy test (WCBP) (e)	Χ	Χ	Χ	Χ	Χ	Χ	Χ	Χ	Χ	Χ	Χ	Χ	Χ	Χ	X	Χ
Laboratory assessments (include liver chemistries)	X	Х	Х	Х	Х	Χ	Х	Χ	Χ	Х	Х	Χ	Х	Х	Х	Х
Serum immunoglobulin (IgA, IgM, IgG)	Х	Х	Х	Х	Х	Х	Х	Χ	Х	Х	Х	Х	Χ	Х	Х	Х
Urinalysis	Х	Х	Χ	Χ	Χ	Χ	Χ	Х	Х	Х	Х	Χ	Х	Х	Х	Χ
Anti-dsDNA/ANA, Complement C3/C4	Х	Х	Х		Х	Х	Х	Χ	Х	Х	Х	Х	Χ	Х	Х	Х
Extractable nuclear antigens (ENAs)		Х			Х				Х				Χ		Х	
PT/PTT	Х	Х			Χ				Χ				Х	Χ	Χ	
Antiphospholipid antibodies																
(aCL, lupus anticoagulant, ±		Χ			Χ				Χ				Χ	Χ	X	
beta-2-glycoprotein-1)		1														
Labs and Biomarkers																
B cells subsets		Χ	Χ				Χ		Χ		Χ		Χ		Χ	Χ

Treatment Phase Procedures	Screening					Trea	atment F	Period –	Arm C ((a)						
(D=Day, W=Week)	(35 to 1 day(s) before D1)	D1, (Base- line)	W4	W6	W8	W12	W16		W26	W28, W32, W36	W40	W44, W48	W52	Unsched- uled Visit (h)	Early Withdrawal Visit (b)	Follow-up Visit (8 weeks post last dose)
BLyS Protein		Х											Х		Х	,
RNA for interferon signature		Х														
Immunogenicity: Belimumab		Х	Χ	Χ	Χ				Χ				Х	Χ	Х	Х
Pharmacokinetics: Belimumab			Χ		Χ				Χ				Х	Х	Х	Х
Genetic sample		Х														
Further Research			•													
B cell subsets (o)		Х	Χ										Х		Х	
B-cell Receptor (I)		Х												Х	Х	
Study Treatment																
Training on use of Autoinjector	Χ	X														
Dispense/Train or Collect Electronic patient diary		Х													Х	
Dispense Belimumab for weekly dosing (SC)		X (f)	Х		Х	Х	Х	Х		Х	Х	Х	Х			
Initiate corticosteroid taper						X (g)										
Target for corticosteroid dose to reach prednisone equivalent ≤5 mg/day									Х							
Study Visit Review Procedures																
AE/SAE review		Х	Х	Х	Х	Χ	Х	Х	Χ	Х	Х	Х	Х	Х	Х	Х
Concomitant medication review (including SLE medications)	Х	Х	Х	Х	Х	Х	Х	Х	Х	Х	Х	Х	Х	Х	Х	Х
Review HCRU and Patient Diary			Х	Х	Χ	Χ	Х	Х	Х	Х	Х	Х	Х	Х	Х	

a. Starting at Week 4 and throughout the study period including follow-up, a study visit time window ± 7 days is acceptable. Note: Every effort should be made to schedule the visit in this window, however if the COVID-19 pandemic situation affects the ability to achieve this then, for those COVID-19 specific instances, the visit window can be expanded to ±28 days.

- b. Early Withdrawal Visit 1-4 weeks after last dose for participants that discontinue and withdraw from the study.
- c. To be conducted prior to clinical assessments.
- d. Survival assessment at Week 52 for participants who withdraw before Week 52.
- e. For WOCBP Serum pregnancy test at Screening; Urine pregnancy test at all other visits, including pregnancy test 16 weeks after last dose of belimumab. The pregnancy test 16 weeks after the last dose of belimumab may be done at home, with the results reported by telephone call to the clinic. See Section 9 for pregnancy test requirements for participants that withdraw.
- f. The first dose of belimumab will be administered at the clinic and the subject needs to stay for 3 hours post dose for observation.
- g. It is recommended that the steroid taper be initiated on Week 12 to reach the target prednisone equivalent of ≤5 mg/day at Week 26, but the taper schedule is at the discretion of the investigator.
- h. Procedures to be performed at Unscheduled Visits are based on reason for Unscheduled Visit, including adverse event or discontinuation of study agent. Please refer to Section 9.4 and to the guidance provided in the Study Reference Manual.
- i. The interim medical history, including SLE medications, should be reviewed prior to randomization to assure that the participant's eligibility has not changed.
- j. Blood samples for a B cell receptor analysis should be obtained in the event of a suspected SLE Flare (refer to footnote I).
- k. To be conducted at US sites only.
- I. To be conducted only at US study sites as part of further research. B-cell receptor samples are also collected at US sites when subjects experience a suspected SLE Flare.
- m. Separate Genetics informed consent as needed per country specific requirements. Genetics informed consent and sample can be obtained any time after baseline.
- n. Independent assessor will perform symptom-driven physical examination to include, at a minimum, assessments of eyes, mouth, skin, lungs, cardiovascular system, abdomen, and extremities (including joints). Independent assessors must have a source document (paper record in the study file) where the findings in the clinical exam and laboratory analyses supporting the scoring of S2K are described.
- o. To be conducted at select European centers.

Table 4 Open-Label Treatment Phase Procedures: Year 2, Arm C

			Treatment	Period – Arm (C (a)				
Arm C Treatment Phase Procedures (W=Week)	W60	W64	W72	W80	W88, W96	W104	Unscheduled Visit (e)	Early Withdrawal Visit	Follow-up Visit (8 weeks post last dose)
Assessments: Clinic									, 
Symptom-driven physical exam, vital signs	Х	Х	Х	Х	Х	Х	Х	X	Х
Weight						Х		Х	
Assessments: Independent Assessor									
SLEDAI-2K: Blinded Assessor (i)		Χ		X		Х	Х	Х	
Assessments: Principal Investigator									
SLEDAI-2K: Investigator	X	Χ	Х	X	X	Х	Х	Х	
C-SSRS Since Last Visit	X	Χ	X	X	X	X	X	Χ	X
Neurological assessment	Х	Х	Х	Х	X	Х	Х	Χ	Х
SLE Flare Index (f)	X	Χ	Х	X	X	Х	Х	Х	
SLICC-ACR Damage Index						Х		Χ	
Physician Global Assessment (PGA)	X	Х	Х	Х	Х	Х	Х	Χ	
Survival assessment (c)						Х			
Assessments: Patient Reported Outcon	nes (PROs)								
Patient Global Assessment (b)		Х	Х			Х		Χ	
FACIT-Fatigue (b)		X	Х			Х		Χ	
Lupus QoL (b)		Х	Х			Х		Χ	
WPAI: Lupus (b)		Х	Х			Х		Χ	
Exit Interview (g)						Х		Χ	
Central Laboratory Tests									
Urine pregnancy test (WCBP) (d)	X	Χ	X	X	X	X	X	Χ	X
Laboratory assessments (include liver chemistries)	Х	Х	Х	Х	Х	Х	Х	Х	Х
Serum immunoglobulin (IgA, IgM, IgG)	Х	Х	Х	Χ	Х	Х	Х	Χ	Х
Urinalysis	Х	Х	Х	Χ	Х	Х	Х	Χ	Х
Anti-dsDNA/ANA, Complement C3/C4	Х	Х	Х	Χ	Х	Х	Х	X	Х

	Treatment Period – Arm C (a)								
Arm C Treatment Phase Procedures (W=Week)	W60	W64	W72	W80	W88, W96	W104	Unscheduled Visit (e)	Early Withdrawal Visit	Follow-up Visit (8 weeks post last dose)
Extractable nuclear antigens (ENAs)	Χ			Х		Х		Χ	
PT/PTT				X		X	Х	Χ	
Antiphospholipid antibodies (aCL, lupus anticoagulant, ± beta-2-glycoprotein-1)	Х			Х		Х	Х	X	
Labs and Biomarkers									
B cells subsets	Χ			X		X		Χ	X
Immunogenicity: Belimumab				X		X	X	X	X
Pharmacokinetics: Belimumab				X		X	Х	Χ	X
Further Research									
B cell receptor (h)						X	Х	Χ	
Study Treatment									
Collect Electronic Diary						Х		Х	
Dispense Belimumab for weekly dosing (SC)	Х	Х	Х	Х	Х				
Study Visit Review Procedures									
AE/SAE review	Χ	Χ	Χ	X	Χ	Х	Х	Χ	X
Concomitant medication review (including SLE medications)	Х	Х	Х	Х	Х	Х	Х	Х	Х
Review HCRU and Patient Diary	Χ	Х	Х	Х	Х	Х	Х	Х	

a. During this study period including follow-up, a study visit time window ± 7 days is acceptable. Note: Every effort should be made to schedule the visit in this window, however if the COVID-19 pandemic situation affects the ability to achieve this then, for those COVID-19 specific instances, the visit window can be expanded to ±28 days.

- b. To be conducted prior to clinical assessments.
- c. Survival assessment at Week 104 for participants who withdraw before Week 104.
- d. The pregnancy test 16 weeks after the last dose of belimumab may be done at home, with the results reported by telephone call to the clinic. .(Argentina only: In addition to pregnancy testing at the specified clinic visits, a urine pregnancy test is to be performed at home at Week 56, Week 68, Week 76, Week 84, Week 92, and Week 100, with the results reported by telephone call to the clinic.)
- e. Procedures to be performed at Unscheduled Visits are based on reason for Unscheduled Visit, including adverse event or discontinuation of study agent. Please refer to Section 9.4 and to the guidance provided in the Study Reference Manual.
- f. Blood samples for a B cell receptor analysis should be obtained in the event of a suspected SLE Flare (refer to footnote h).
- g. To be conducted at US sites only.
- h. To be conducted only at US study sites. B-cell receptor samples are also collected at US sites only when subjects experience a suspected SLE Flare.
- i. Independent assessor will perform symptom-driven physical examination to include, at a minimum, assessments of eyes, mouth, skin, lungs, cardiovascular system, abdomen, and extremities (including joints). Independent assessors must have a source document (paper record in the study file) where the findings in the clinical exam and laboratory analyses supporting the scoring of S2K are described.

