Serum Sickness: Serum sickness has been associated with rituximab in autoimmune	Rituximab: The incidence of serum sickness associated with rituximab in pSS studies has	Immunogenicity will be evaluated with periodic assessment over the course of the study.	
indications [Meijer, 2010]. There is a potential risk for increased immunogenicity due to cross reactivity which could lead to increased frequency of	ranged from 6-38% [Carubbi, 2014]. Administration of belimumab and rituximab may result in infusion and hypersensitivity reactions, which can be severe and can be fatal. Delay in	A pre-medication regimen will be given before each rituximab/rituximab placebo infusion: methylprednisolone 100 mg IV, an antihistamine and acetaminophen or equivalent.	
hypersensitivity reactions, particularly of the delayed type.	the onset of serious hypersensitivity reactions can occur. Both rituximab and belimumab have been associated with delayed type non-acute Hypersensitivity reaction (HSR)/serum sickness, although no relationship to Anti-drug Antibody (ADA) has been established.	Subjects should remain under clinical supervision for 3 hours after completion of the first belimumab injection and the rituximab/placebo infusions. Should symptoms of acute hypersensitivity occur, an extended period of monitoring may be appropriate, based on	
	Belimumab and Rituximab Coadministration: Incidences of hypersensitivity and infusion reactions have been noted to be higher with co- administration vs. mono-biologic therapy but no	clinical judgement. If subjects are to receive belimumab after 4 consecutive weeks of not receiving belimumab, the first belimumab dose must be administered in the clinic and subject	

Potential Risk of Clinical Significance	Summary of Data/Rationale for Risk	Mitigation Strategy	
Investigational Product (IP): Beli	Investigational Product (IP): Belimumab (GSK1550188), Rituximab, and Belimumab and Rituximab Coadministration		
	association with ADA has been established [Weinblatt, 2006].	should remain under clinical supervision for 3 hours after the completion of the dose.	
		Patients will be given an alert card for HSR and delayed HSR/serum sickness.	
Malignancy:			

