7.6. Treatment Compliance

• The first dose of belimumab will be administered by the participant at the clinical site under medical supervision. (Participants may be assisted in administration of their SC dose of belimumab at this first dose and with subsequent doses.)

Participants will remain in the clinic for at least 3 hours for observation. The date and time of the dose administered in the clinic will be recorded in the Patient Diary.

NOTE-1: If a participant misses a dose of belimumab on the scheduled day of administration, instruct the participant to self-administer the missed dose as soon as possible during that dosing week. If subject did not self-administer the dose by end of the weekly dosing period, SKIP that dose. The participant should not administer two doses on the same day and two doses should not be administered to make up for a dose missed for a full 7 day dosing window. Thereafter, the subject can resume self-administering belimumab weekly on their usual day of administration.

NOTE-2: If a participant has administered a partial dose or was unable to completely self-administer a dose of belimumab due to malfunction of the autoinjector or user error, instruct the subject to SKIP additional attempts and not re-inject for that week's belimumab dose. Thereafter, the subject should resume self-administering belimumab weekly on their usual day of administration during the following weekly dosing period. The participant should not self-administer 2 doses on the same day, even if they believe that they did not receive any medication from the first administration attempt. (See Section 9.7.8 - Device Malfunction).

NOTE 3: Participants who miss 4 or more consecutive doses of belimumab must receive the next dose of belimumab in the clinic and remain in the clinic for at least 3 hours for observation as with the initial belimumab dose.

The site should contact the Medical Monitor if participants miss 8 or more consecutive doses of belimumab to evaluate continuation in the study.

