- When participants self-administer study treatment at home, compliance with belimumab will be assessed through review of the self-injection patient diary with each participant during site visits and documented in the source. A record of the number of belimumab autoinjectors dispensed to and taken by each participant must be maintained and reconciled with study treatment and compliance records. Treatment start and stop dates, including dates for treatment delays will also be recorded in the eCRF.
- Rituximab or rituximab-placebo will be administered IV to participants at the site or
 infusion center, following administration of the premedication regimen.
 Administration of the premedication regimen and the rituximab or rituximab-placebo
 will be documented in the source documents and reported in the eCRF, including
 whether the full infusion was administered and over what period of time. Study
 participant identification will be confirmed at the time of dosing by a member of the
 study site staff other than the person administering the study treatment.

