1. INTRODUCTION

This RAP addendum is supplemental to the RAP (Dated: 05/AUG/2020), and the first RAP addendum (Dated: 08/OCT/2020). It is based on protocol amendment 04 (Dated: 30/APR/2020) of study 205646.

The main purpose of this addendum is to list an abridged set of outputs that will be produced for the final study report. These changes are being made following the first database lock and primary analyses at the end of Year 1 of the study.

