3.2. Final Analyses

There will be two database locks for this study, corresponding to the primary analyses and the end of study analyses. The primary analyses will include data up to the 52 week visits for the primary endpoint.

The primary analyses will be performed after the completion of the following sequential steps:

1. All subjects have completed the Week 52 visit (or Early Withdrawal visit for those subjects who withdraw from the study during Year 1).
2. All required database cleaning activities have been completed and final database release (DBR) has been declared by Data Management.
3. All criteria for unblinding the randomisation codes have been met, including:
 - Review of Protocol Deviations through Week 52
 - Adjudication of AESI through Week 52
 - Review of treatment failures through Week 52
4. Randomisation codes have been distributed according to RandAll NG procedures.
5. Database freeze (DBF) has been declared by Data Management.

A final analysis will be conducted following the last subject completion of year 2 (including all 8 week-follow-up visits) when all required database cleaning activities have been completed and final database release and database freeze has been declared by Data Management as described in Steps 2, 3 and 5 above

This RAP details the planned analysis for both database locks, with the expectation of an observed treatment benefit at Week 52. If the Week 52 reporting does not identify a treatment benefit, an abridged set of analysis may be conducted at the end of the study, which will be detailed in a RAP amendment or RAP addendum.

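### Observation after each rituximab/placebo infusion is 1 hour in the Schedule of Activities but 3 hours in the risk-mitigation table, and no section says which prevails

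*Protocol*

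**What the plan says.** - **Protocol Section 2, Table 1 footnote j** (rituximab or rituximab-placebo, Weeks 4 and 6, Arms A and B): "the subject needs to stay in clinic for 1 hour post dose for observation".
- **SAP Section 15.2, Table 5 footnote j**: a copy of the same schedule, also 1 hour.
- **Protocol Section 3.3.1, Mitigation Strategy** for infusion and hypersensitivity reactions: "Subjects should remain under clinical supervision for 3 hours after completion of the first belimumab injection and the rituximab/placebo infusions".
- **Protocol Section 2, Table 1 footnote i**: "The first dose of belimumab will be administered at the clinic and the subject needs to stay for 3 hours post dose for observation".
- **Protocol Section 7.6**, on the first belimumab dose: "Participants will remain in the clinic for at least 3 hours for observation". For the infusions, the section covers premedication and documentation but gives no observation period.
- **Protocol Section 9** says that the Schedule of Activities summarizes procedures and timing, and that adherence to design requirements, the schedule included, is required. It does not say which section governs if two differ.

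**The concern.** Section 3.3 introduces 3.3.1, together with Section 8.2, as the protocol's mitigation strategy, adopted because experience with the combination is very limited. The benefit-risk conclusion in 3.3.3 relies on the measures put in place to reduce risk. Section 3.3.1 warns that giving the two agents may "result in infusion and hypersensitivity reactions, which can be severe and can be fatal".

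Site staff usually work from the schedule and its footnotes. If they did so here, participants could leave the clinic 2 hours earlier than the mitigation strategy intends. What is at stake is delivery of a safety measure on which the benefit-risk case rests, not the efficacy result.

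**Working it through.** The main check is a comparison of texts; the arithmetic only sizes it.

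**1. Do the two texts cover the same event?** Yes. The 3-hour sentence in 3.3.1 names the rituximab/placebo infusions as well as the first belimumab injection, so it cannot be read as belimumab only. Footnote j is attached to the infusion row at Weeks 4 and 6, and to unscheduled visits used to make up a missed infusion.

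| Event | Section 3.3.1 | Table 1 footnote | Section 7.6 |
|---|---|---|---|
| First belimumab dose | 3 h | 3 h (footnote i) | at least 3 h |
| Each rituximab/placebo infusion | 3 h | 1 h (footnote j) | not stated |

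The belimumab row agrees throughout. Only the infusion row conflicts.

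**2. Is there a rule that settles it?** None appears in either document. Section 9 points sites to the schedule without ranking it above other sections, Section 7.6 is silent on the infusions, and the SAP copy only repeats footnote j.

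**3. How many infusions are covered?** Allocation is 1:2:1, so Arms A and B together hold 3/4 of those randomized, with two infusions planned each.

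- Target: 280 × 3/4 = 210 participants; 210 × 2 = 420 infusions.
- Maximum: 320 × 3/4 = 240 participants; 240 × 2 = 480 infusions.

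**4. How large is the gap?** 3 h − 1 h = 2 h per infusion, or 4 h per participant. Over all planned infusions this is 420 × 2 = 840 h at target and 480 × 2 = 960 h at the maximum.

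**5. Are infusions still to come?** SAP Section 3.2 holds the primary analysis until every participant has had a Week 52 visit or, after withdrawing in Year 1, an Early Withdrawal visit. The end-of-study SAP addendum, signed in July 2021, says of its contents: "These changes are being made following the first database lock and primary analyses at the end of Year 1 of the study". The Week 4 and Week 6 infusions were therefore over by that lock.

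**The case against.** The best defence is that the two texts can be reconciled. Footnote j uses the language of requirement, while 3.3.1 says what should happen. With Section 9's demand for adherence to the schedule, that could mean a 1-hour minimum and a 3-hour recommendation. The wording does differ in force, and a site that kept participants for 3 hours met both texts. But the protocol never sets out this two-tier reading, and adopting it would make a stated mitigation optional.

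It can also be said that the documents do not show which period was intended. The amendment history records that infusion-monitoring information was added in Amendment 02, but the entry names no period. The Study Reference Manual and the local rituximab label were not available and may address the point. This stands as a limit on certainty. It does not weaken the case for 3 hours, the one period that meets both texts; choosing 1 hour would mean weakening 3.3.1, and the documents give no clinical argument for that.

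Other protections apply whichever period is used: premedication, longer monitoring on clinical judgement if acute symptoms appear, and patient alert cards. They reduce the likely consequence but do not remove the conflict.

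Three stronger readings are tempting and not supported:

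- **That participants were under-observed.** The totals above are planned infusions. Nothing shows how many sites used 1 hour, or what harm the shorter stay would cause.
- **That a calendar date can be fixed for the last infusion by counting back from the lock.** Early withdrawers need not have reached Week 52, and the visit window may widen to ±28 days in COVID-19-specific instances. Only completion by the lock is supported.
- **That the trial result is affected.** Footnote j applies alike to Arms A and B, and observation time does not enter the endpoint.

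**Conclusion.** The inconsistency is real and present in current text: 1 hour against 3 hours for the same infusions, with no order of precedence. It spans 420 planned infusions at target enrolment and 480 at the maximum, with a 2-hour difference at each. This takes post-dose in footnote j to run from the end of the infusion, as 3.3.1 does, and assumes that no document outside this set resolves the conflict.

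Severity is minor. It is a contradiction about safety conduct whose effect is now retrospective. Alpha, power and the primary comparison are unchanged.

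**What to change.** Change footnote j of Protocol Table 1 to 3 hours after each rituximab/placebo infusion, and change its copy in SAP Section 15.2 to match. This aligns the schedule with 3.3.1 and with the period already used for the first belimumab dose.

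For any infusion given under the corrected text, the cost is 2 more clinic hours. With the scheduled infusions finished, the cost in this trial is editorial. Protocol Appendix 4 requires ethics approval before design changes are implemented, so the correction can go into any later amendment.

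Sites need not be asked to recover the observation times they applied. Section 7.6 asks for "whether the full infusion was administered and over what period of time" but not the time observed afterwards, so retrieval could mean going back to source records.

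Two other mismatches should be raised separately and lend no weight to this point: the action on life-threatening infection (Protocol 3.3.1 against 8.2), and the sirolimus maximum (2 mg/kg/day in Protocol 7.7.1.4 against 2 mg/day in SAP 15.6.9 and 15.6.15.6).
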